8.3.3. Treatment for Patients Randomly Assigned ARI-ORAL

8.3.3.1. Starting Dose of ARI-ORAL

The recommended starting dose for ARI-ORAL should be determined per the prescribing information ([Abilify USPI](#)). Patients will start ARI-ORAL as soon as possible, after filling their ARI-ORAL prescription at the local pharmacy. The reasons for dosage changes will be documented.

8.3.4. Treatment for Patients Randomly Assigned to AL-LAI

8.3.4.1. Starting dose of AL-LAI

The recommended starting dose for AL-LAI should be determined per the prescribing information ([Aristada USPI](#)).

8.3.4.1.1. Initiation Regimen

The preferred method of initiating AL-LAI is the one-day initiation regimen consisting of a single-dose injection of 675 mg AL-NCD IM plus a single 30 mg oral aripiprazole.

8.3.4.1.2. Exceptions to the One-day Initiation Regimen

The alternative to the one-day initiation regimen is prescribing 21-days of oral aripiprazole in conjunction with the first injection of AL-LAI. This method will be allowed but needs to be documented, with reasons including:

1. Presence of genetic or drug-drug interactions regarding CYP interactions that exclude one-day initiation regimen
2. Patient refusal to accept the one-day initiation regimen (but agrees to accept the AL-LAI starting dose during the same visit)

8.3.4.1.3. Timing of the First AL-LAI Treatment

When starting with the one-day initiation regimen, the starting dose of AL-LAI can be given within 60 minutes of AL-NCD. Patients will also be asked to take the 30 mg aripiprazole tablet with the injections, but clinicians will have the option of giving the oral dose to the patient to be taken at bedtime if the patient has family members willing to supervise.

8.3.5. Does Adjustments

8.3.5.1. ARI-ORAL Dose Adjustments

Dose adjustments of ARI-ORAL should be made per prescribing recommendations ([Abilify USPI](#)).

8.3.5.2. AL-LAI Dose Adjustments

Patients who have successfully received three or more monthly AL-LAI without significant tolerability problems will be eligible to change to a 1064 mg/two month interval regimen. Dose adjustments should be made per prescribing information ([Aristada USPI](#)). The following are also required to dose adjust:

- Patient request with clinician assent
- Clinician recommendation

9. STUDY DRUG MATERIALS AND MANAGEMENT

9.1. Storage

Study drug must be stored in a locked area at 20°C to 25°C (68°F to 77°F); excursions between 15°C and 30°C (59°F and 86°F) are permitted.

Note that AL-NCD has a specific instruction “Do not freeze” on its packaging.

9.2. Handling of Study Drug

9.2.1. AL-LAI Medication Group

AL-LAI and AL-NCD will be provided by Alkermes, Inc. and should be shipped to:

UCLA Investigational Drug Pharmacy
Ronald Reagan UCLA Medical Center
Dept. Of Pharmaceutical Services
[name]
[name]

[contact]

AL-LAI and AL-NCD will be stored and dispensed by the UCLA Investigational Drug Pharmacy. Both will be stored in a locked cabinet after it is dispensed up until the time of injection.

9.2.2. ARI-ORAL Medication Group

The ARI-ORAL group will be given paper or electronic prescriptions, or the prescription may be telephoned to, or faxed to, the pharmacy of the patient's choice. Prescriptions will typically be for 30 day supplies, unless otherwise indicated by the treating psychiatrist. Side-effect medications, such as anti-parkinsonians, beta-blockers, and benzodiazepines will also be billable through the voucher system. The patient will be provided a payment coupon that s/he will present to the pharmacy. The payment coupon will direct the pharmacist to Alkermes for reimbursement. Subsequent refills will not require a new coupon. Patients will be seen by the Aftercare Research Program clinical team every two weeks. This prescribing routine as outlined for this study is consistent with standard pharmacologic treatment for patients in clinical care at the same site who are prescribed oral antipsychotic medication.

Deliberate over-prescribing or stockpiling is not permitted. Patients who are discontinuing ARI-ORAL will be allowed to overlap antipsychotic for a maximum of one month; otherwise co-prescribing two oral antipsychotics is not allowed.

10. ASSESSMENT OF EFFICACY

10.1. Primary Endpoint

10.1.1. Primary Endpoint Measurements

The primary endpoint will be time to first positive symptom exacerbation and/or relapse following a period of relative remission of psychotic symptoms based on expanded 24-item version Brief Psychiatric Rating Scale (BPRS) (published UCLA relapse criteria (Nuechterlein et al, 2006) that are summarized in Section 7.4.6.

10.1.2. Primary Endpoint Rationale

The expanded BPRS (Ventura et al, 1993) will be rated every two weeks, with each item rated from 1 (not present) to 7 (extremely severe). Positive symptom exacerbation or relapse will be identified based on increases of the BPRS items Unusual Thought Content, Hallucinations, or Conceptual Disorganization using computer scoring algorithms (Nuechterlein et al, 2006). The three scoring categories considered to be a psychotic symptom return are: “Remission Followed by Relapse”, “Remission Followed by Significant Exacerbation”, or “Persisting Symptoms Followed by Significant Exacerbation.” These definitions do not consider other aspects of outcome often part of “treatment failure” definitions, such as: hospitalization or increased treatment to prevent hospitalization; harm to self, others, or property; arrest; or treatment discontinuation, as these other negative outcomes might not be secondary to psychotic symptoms per se. These classifications have been shown to be sensitive measures of the return of psychotic symptoms and differentiated oral and long-lasting injectable treatment groups in our previous research (Subotnik et al, 2015). Patients in the proposed study will continue in the protocol even if a psychotic relapse or exacerbation occurs, although the medication regimen might change at the discretion of the Aftercare Research Program treating psychiatrist. Our experience has been that the majority of psychotic exacerbations or relapses can be managed on an outpatient basis unless the patient has concurrent imminent suicidality, and often the prescribed medication does not change (although the dosage might). Continuing patients in the protocol after a return of symptoms will allow us to assess secondary outcomes at the 6- and 12-month points.

10.2. Secondary Endpoints

10.2.1. Secondary Endpoint Measurements

The secondary endpoints of this study are:

- GFS: Role
- Overall Composite T-score MCCB

10.3. Exploratory Endpoints

10.3.1. Exploratory Endpoint Measurements

The exploratory endpoints of this study are:

- Heinrichs-Carpenter QLS

- PSP
- CGI-S
- SANS
- SUMD-R
- GASS
- Modified MSQ
- SES
- Family Caregiver Medication Administration Hassles scale
- Modified Version of the ACD

11. ASSESSMENT OF SAFETY

11.1. Definition of Adverse Event

An AE is any untoward medical occurrence in a patient or clinical investigation patient who has been administered a pharmaceutical product. The occurrence may or may not have a causal relationship with the investigational treatment, may include any clinical or laboratory change that does not commonly occur in that patient and is considered clinically significant.

Pregnancy is not considered an AE, although a patient will be withdrawn from the study if a pregnancy occurs. The pregnancy, including a partner's pregnancy, must be reported to Alkermes, and additional follow-up may be required.

11.2. Definition of Serious Adverse Events

An SAE is any AE, occurring at any dose and regardless of causality, that:

- Results in death
- Is life-threatening. The patient is at immediate risk of death from the reaction as it occurs. This does not include reaction that, had it occurred in a more severe form, might have caused death
- Requires inpatient hospitalization or prolongation of existing hospitalization
- Results in persistent or significant disability/incapacity (eg, a substantial disruption of a person's ability to conduct normal life functions)
- Is a congenital anomaly/birth defect

Important medical events that may not result in death, be immediately life threatening, or require hospitalization may be considered to be SAEs when, based upon appropriate medical judgment, may jeopardize the patient and may require intervention to prevent one of the other outcomes listed above.

Admission to a hospital or an inpatient unit for a non-medical reason (i.e., social stay admission) during the study in the absence of untoward medical occurrence will not be considered as an SAE.

Hospitalization due to worsening of behavioral health related issues should be reported as an SAE.

11.3. Reporting of Serious Adverse Events and Pregnancy

Investigator is responsible for timely reporting of Adverse Drug Experiences, Serious Adverse Drug Experiences and pregnancy in a Study patient to the Food and Drug Administration (FDA), Institutional Review Board (IRB), data safety monitoring board, Institution, grant agency, etc. as applicable to the Study and according to FDA, Institution and/or grant agency guidelines and procedures.

12. STATISTICS

12.1.1. Sample Size Considerations

Ninety first-episode patients will be randomized (1:1) fashion to either AL-LAI or ARI-ORAL, and based on our previous RCT, assume a 20% attrition rate over 12 months. Statistical power considerations are based on the effect sizes observed when comparing long-acting injectable risperidone vs. oral risperidone (survival analysis for psychotic relapse: 5% relapse in the risperidone long-acting injectable group and 33% relapse in the oral risperidone group). On the basis of hazard function rates of 5.0% (AL-LAI) and 33% (ARI-ORAL), the study has 87% power ($\alpha=0.05$). On a more conservative basis of hazard function rates of 7.5% (AL-LAI) and 33% (ARI-ORAL), the study has 78% power ($\alpha=0.05$) (Table 6).

For the secondary hypothesis for the relative changes in the MCCB Composite score and the GFS: Role, we will use a two-sided significance level of $\alpha=.025$ to account for type 1 error inflation. For the MCCB Composite score, assuming a within-patient correlation between repeated measurements of $r=0.89$ (based on a prior study), the proposed design provides us sufficient power ($>=0.80$) for Group X Time interaction effects as small as Cohen's $f=0.09$. Based on our previous work, we anticipate a medium effect size (Cohen's $f=0.25$ or $d=0.50$), and this design provides a power of >0.99 for an effect of this size. For the GFS rating, if we assume a within-patient correlation of $r=0.5$, with $\alpha=0.025$, our GLMM will have 80% power to detect an interaction corresponding to an effect size of $f=.20$. Based on a prior study, we anticipate an effect size of $f=0.32$ or $d=0.63$ for the GFS: Role ratings, for which we would have $>99\%$ power.

Thus, for both primary and secondary outcome measures we will be able to detect differential treatment effects based on our proposed design and expected sample size.

Table 7: Power Calculations by Analysis with N=35 Each Group (N=28 at completion)

Clinical assumption for each group			Power	Alpha
Primary Analyses	Hazard ratio between the two groups	Difference in hazard functions similar to that of our previous RCT: Long-acting injectable: 5%, oral antipsychotic: 33%	87%	.05
		For rates of hazard function rates of 7.5% (AL-LAI) and 33% (ARI-ORAL)	78%	
Secondary Analyses: MCCB Overall Composite score	change from BL in MCCB Overall Composite score	Based on our previous work, we anticipate a medium effect size (Cohen's $f=.25$ or $d=.50$)	>99%	.025
Secondary Analyses: GFS Role Functioning	Change from BL in GFS Role Functioning	Based on a prior RCT, we anticipate an effect size of $f=.32$ or $d=.63$ for the GFS: Role ratings.	>99%	.025

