12.4. Efficacy Analysis

The primary hypothesis, that the hazard function (i.e. the risk of an event per unit of time) of the two medication groups differs between AL-LAI than the ARI-ORAL group, will be examined in a Cox regression analysis on the time to first relapse. We will include medication group membership, participation status in the NIMH exercise study, and length of stabilization period as predictors in the model.

For the secondary hypotheses involving the MCCB composite score, the GFS: (Role) we will use general linear mixed models (GLMMs). We will include participation status in the NIMH exercise study, medication group as a between-patient variable and time as a within-patient

variable in the model, and time*group as a within-between interaction term. Additionally, we will include length of stabilization period as person level time invariant covariate. The primary effect of interest is the difference in the pattern of change over time of the dependent variable between the medication groups, i.e. the time*group interaction term. GLMMs properly account for correlations induced by repeated measurements within patients and automatically handle missing data, producing unbiased estimates as long as observations are missing at random. The GLMM will use Satterthwaite's approximation to estimate degrees of freedom for the tests of the fixed and random effects, and model the variance-covariance matrix as a Toeplitz matrix. If this assumption does not lead to convergence we will instead use compound symmetry. The secondary analyses will compare the change in the MCCB Composite score and GFS: (Role) ratings between the two medication groups over the 12-month study period.

The data analyses for the exploratory measures will parallel those of the secondary measures.

All statistical tests and confidence intervals, unless stated otherwise, will be two-sided and will be set at $\alpha=0.05$.

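### The fixed 0.025/0.025 split of the two secondary endpoints is valid, but Holm would give at least as much power at the same family-wise error; the gain is about 1 point at the plan's stated power and about 10 to 11 points at 80%

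*Combined protocol and SAP*

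**What the plan says.** For the two secondary endpoints, section 12.1.1 sets a two-sided level of 0.025 each, "to account for type 1 error inflation". The Synopsis says the same, and Table 7 shows .025 for each endpoint. No section gives an order of testing, a step-down rule or a way to pass alpha from one endpoint to the other.

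Section 12.4, which holds the analysis rules, does not repeat the 0.025. It gives a general default: "All statistical tests and confidence intervals, unless stated otherwise, will be two-sided", at 0.05.

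Power in 12.1.1 is stated at 0.025:

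- **MCCB:** at least 0.80 for "Group X Time interaction effects as small as Cohen's $f=0.09" and, at the anticipated f=0.25, "this design provides a power of >0.99 for an effect of this size".
- **GFS: Role:** 80% at f=0.20 and more than 99% at the anticipated f=0.32.

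**The concern.** Under the fixed split each endpoint faces 0.025 whatever the other shows. If one endpoint is clearly positive and the other has a p-value between 0.025 and 0.05, the second is declared negative. Holm would declare it positive and still hold the family-wise error of the pair at 0.05. What is at stake is therefore power on a secondary claim. The validity of any claim is not in question.

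**Working it through.** **Inputs from the documents.** Alpha is 0.025 two-sided per endpoint (12.1.1, Table 7). The within-patient correlation is 0.89 for MCCB and 0.5 for GFS: Role (12.1.1). There are 3 MCCB visits (Synopsis, Table 2) and 5 GFS: Role visits (Table 2 footnote). Completers number 36 per group in the Synopsis (N=72) but 28 per group in the heading of Table 7 (N=56), so both are shown. **Assumption:** the correlation between the two test statistics is not given; 0 and 0.3 are used.

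**Step 1: the plan's own power.** For the group-by-time interaction, take a noncentral F with λ = f²·N·m/(1−r) and df = (m−1) and (N−2)(m−1), at alpha 0.025.

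- MCCB, f=0.09, m=3, N=56: λ = 0.0081·168/0.11 = 12.4; power 81.8%. With N=72: λ = 15.9; power 91.5%. The stated 80% matches the Table 7 sample size.
- MCCB, f=0.25, m=3: about 100% at either size.
- GFS: Role, f=0.32: 99.3% or higher for every N and number of visits tried. The stated figure of more than 99% reproduces.
- GFS: Role, f=0.20: the stated 80% is not matched. N=56 gives 75.2% (2 visits), 85.3% (3 visits) and 95.7% (5 visits); N=72 with 5 visits gives 99.0%.

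**Step 2: family-wise error of the pair.** If both endpoints are null, the two procedures have the same error: at most 0.025 + 0.025 = 0.05, and 1 − 0.975² = 0.0494 if independent. If one is null and the other has 80% power (independent tests), the null endpoint's error is 0.025 under the split and 0.025 + 0.025·0.80 = 0.045 under Holm. As the other endpoint's power approaches 100%, the Holm figure approaches 0.05 and does not pass it.

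**Step 3: power to show both.** The split needs both p<0.025. Holm needs both p<0.05 with at least one below 0.025:

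P(Holm shows both) = P(both p<0.05) − P(both p between 0.025 and 0.05).

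For power P at 0.025 the noncentrality is 2.2414 + z(P).

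- *80% each, independent.* Noncentrality 2.2414 + 0.8416 = 3.083, so power at 0.05 is 86.9%. Split: 0.80² = 64.0%. Holm: 0.8693² − (0.8693 − 0.80)² = 75.1%. Gain 11.1 points. At correlation 0.3: 66.6% to 76.6%, gain 9.9.
- *99% each, independent.* Power at 0.05 is 99.5%. Split: 0.99² = 98.0%. Holm: 99.1%. Gain 1.1 points; 1.0 at correlation 0.3.
- *Powers recomputed in step 1 for the anticipated effects:* gain at most 0.4 points.
- *Powers recomputed for the smallest detectable effects, independent:* N=56 with 3 visits each, 69.8% to 80.0% (about 10 points); N=72 with 3 and 5 visits, 90.6% to 94.7% (about 4 points).
- *Largest gain over all effect sizes, independent:* about 12.7 points, near 65% power each.

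**Step 4: sensitivity cases, both assumed.** Replace the plan's multi-visit interaction by a single Month 12 difference in change, with 36 per arm and noncentrality d·√18/√(2(1−r)).

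- d=0.50 (MCCB) and 0.63 (GFS: Role): noncentralities 4.52 and 2.67. GFS: Role power is 66.7% at 0.025. Power for both goes from 65.9% to 75.8%, a gain of about 10 points.
- Smaller effects chosen for illustration and not in the documents, 0.30 and 0.50: GFS: Role power is 45.2% at 0.025. Power for both goes from 30.8% to 42.6%, a gain of about 12 points (independent tests).

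**The case against.** The strongest reply is that nothing in the plan is wrong. An equal split fixed in advance is valid, conservative and stated alike in the Synopsis, 12.1.1 and Table 7. At the effects the plan anticipates there is almost no power left to gain. The split also buys something: a simple 97.5% interval for each endpoint, and a 2.5% error for each endpoint on its own. All of this stands, and it makes the point an efficiency improvement and not a correction.

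Three stronger readings are tempting, and the documents do not support them.

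- *The plan gives up some 11 points of power on its own assumptions.* It does not. That figure belongs to 80% power on each endpoint, which 12.1.1 attaches to the smallest detectable effects. At the anticipated effects the stated power exceeds 99%.
- *GFS: Role really has 67% power.* That figure comes from treating d=0.63 as one Month 12 contrast. The plan tests the time-by-group interaction over all visits, and its figure of more than 99% reproduces on that test. Table 7 does describe the measure as change from baseline, so the single-contrast reading is usable as a sensitivity case, but it does not refute the stated power.
- *Section 12.4 contradicts 12.1.1 on alpha.* Its 0.05 default applies only where nothing else is stated, and 12.1.1 states 0.025.

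Against the objection, the anticipated effects rest on prior work, and true effects may be smaller. In that case Holm helps; if power really exceeds 99%, switching loses no power.

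**Conclusion.** The point holds as a cheap improvement. That Holm never rejects less than the fixed split, and keeps the pair's family-wise error at or below 0.05, does not depend on any effect size or correlation. The size of the gain does:

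- about 1 point or less if each endpoint has the stated power of more than 99%;
- about 10 to 11 points if each has 80% (correlation 0 to 0.3 assumed);
- about 10 to 12 points if effects are smaller than anticipated or d is read as a single Month 12 difference in change, both of which are assumptions.

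The 0.05 here covers the two secondary endpoints only.

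**What to change.** In the Synopsis, 12.1.1 and 12.4, before outcome data are seen, replace the fixed level with: *order the two secondary p-values; test the smaller at two-sided 0.025; if significant, test the larger at two-sided 0.05 (Holm).* Keep the 0.025 power figures and label them as the conservative case, in Table 7 as well. This also puts the multiplicity rule into 12.4, where it is now absent.

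The change needs no more patients or visits. Its costs are two. Intervals that match the stepwise test are less simple than fixed 97.5% intervals, so the text should say which intervals will be reported. And a null endpoint's own error can rise from 2.5% to 5% when the other endpoint is positive.

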12.2. General Statistical Methodology

12.2.1. Intent-to-Treat Population

The Intent-to-treat (ITT) population will include all patients in the AL-LAI group who received at least one dose of AL-LAI, and all patients in the ARI-ORAL antipsychotic medication group who filled at least one prescription of ARI-ORAL after random treatment assignment. This population will be used for efficacy and safety analyses.

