Criteria for Efficacy Evaluation: Primary Endpoint The primary endpoint will be time to first positive symptom exacerbation and/or relapse following a period of absence or relatively low levels of psychotic symptoms based on the expanded 24-item version Brief Psychiatric Rating Scale. Secondary Endpoints Functional assessment: The Role ratings on the Global Functioning Scale (GFS: Role) will serve as the measure of functional outcome. The GFS: ROLE will be administered every three months throughout the 12-month Treatment period. Cognitive assessment: The Overall Composite T-score from the MATRICS Consensus Cognitive Battery (MCCB) will be the overall index of cognitive performance. The MCCB will be administered every six months throughout the 12-month Treatment period. Exploratory Endpoints Endpoints include Quality of Life, negative symptoms, self-reported awareness of having a mental disorder, service engagement, prolactin-related side effects, treatment satisfaction, and family/caregiver medication administration burden. Safety Assessments Extrapyramidal symptoms will be assessed on three scales (Abnormal Involuntary Movement Scale, Barnes Akathisia Rating Scale, and the Extrapyramidal Symptom Rating Scale). Adverse events (including serious and AEs of special interest), and suicidality will be monitored.
Statistical methods: Sample Size Considerations: Ninety first-episode patients will be randomized (1:1) fashion to either AL-LAI or ARI-ORAL, and based on our previous RCT, assume a 20% attrition rate over 12 months. 45 randomized patients (36 completers) in each group provides at least 80% power. Statistical power considerations are based on the effect sizes observed when comparing long-acting injectable risperidone vs oral risperidone (survival analysis for psychotic relapse: 5% relapse in the risperidone long-acting injectable group and 33% relapse in the oral risperidone group). On the basis of hazard function rates of 5.0% (AL-LAI)

and 33% (ARI-ORAL), the study has 87% power ($\alpha=0.05$). On a more conservative basis of hazard function rates of 7.5% (AL-LAI) and 33% (ARI-ORAL), the study has 78% power ($\alpha=0.05$).

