6.3. Discontinuation of Assigned Medication

If the randomly assigned medication must be discontinued and/or switched to a different antipsychotic medication, the patient may remain in the study until the 12-month assessment point. End of Assigned Treatment assessment point measures will be completed as close to and if possible, just prior to, the discontinuation/switch. Decision to switch medication will be recorded on a modified Clinical Antipsychotic Trials of Intervention Effectiveness (CATIE) All-Cause Discontinuation (ACD) assessment completed by the treating psychiatrist (Stroup et al, 2003). The switch to another antipsychotic medication will be guided by clinician judgment using the medication selection recommendation adapted from the oral antipsychotic guidance used in the RAISE study (Kane et al, 2015). The date the new medication is prescribed will be recorded and used in the analyses. Patients who choose to discontinue study medication will be allowed to re-

initiate study medication at any time during the 12-month follow-up. All other regular assessments will be completed throughout the remainder of the 12-month study.

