6.4. Over-enrollment of Patients

Over-enrollment (beyond 90 patients) will occur to ensure that there are at least 14 patients who had a relapse in the 12-month Treatment period.

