7.2.2. Initiation of AL-LAI Treatment Arm after Randomization

Initiation of AL-LAI will begin with a one-day initiation regimen (675 mg AL-NCD and 30 mg oral aripiprazole) per prescribing information ([Initio USPI](#)) unless the alternative initiation is selected (see Section 8.3.4.1.2). Dosing of AL-LAI will be flexible based on clinician judgment per prescribing information ([Aristada USPI](#)). The first AL-LAI injection may be administered on the same day as the one-day initiation regimen or up to ten days thereafter. Treatment with AL-LAI can be initiated at a dose of 441 mg, 662 mg or 882 mg administered monthly, 882 mg administered every six weeks or 1064 mg administered every two months. Patients assigned to the AL-LAI treatment arm will return to the clinic for injections during scheduled visits.

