7.4.9. Safety Assessments

7.4.9.1. Overview of Safety Assessment Procedures

Each patient will have a treating psychiatrist who is a part of the clinical team for UCLA Aftercare Research Program. The psychiatrist will be responsible for the medical and psychopharmacologic management of patients. The one-on-one medication assessment appointments are scheduled at least monthly, and may be more frequent as per the clinical status and needs of the individual patient. The treating psychiatrists have specialty practice experience in schizophrenia and psychotic disorders, and will be trained in all of the ongoing safety assessments for the study, including:

- Extrapiramidal symptoms (Abnormal Involuntary Movement Scale [AIMS], Barnes Akathisia Rating Scale [BARS], and the Extrapiramidal Symptom Rating Scale [ESRS-A])
- Columbia Suicide Severity Rating Scale (C-SSRS)
- AE collection
- Serious adverse event (SAE) reporting

The treating psychiatrists also attend the UCLA Aftercare Research Program weekly case conferences where the entire clinical team, including the clinical assessors, meets to review the clinical status of all patients in the program. Patients will be reviewed for any SAEs or other

clinical changes on a weekly basis. However, the BPRS assessments that are the basis of the relapse criteria are not specifically reviewed within the case conferences, but salient clinical information gleaned from the biweekly BPRS ratings will be shared at that time and will be used along with all other relevant clinical information for further medication management and patient treatment decisions.

Semi-annual review of all safety assessment responses will be conducted by a Data and Safety Monitoring Committee at UCLA who are not study investigators per the UCLA IRB standards.

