7.4.12. Adverse Event Monitoring

Continuous monitoring of AEs will take place from the time a patient signs the informed consent document until the completion of the final study visit. Additional information on the assessment of safety is provided in Section 11.

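### The set labelled intent-to-treat drops randomised patients by post-randomisation tests that differ by arm, and it is the only efficacy and safety set

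*Combined protocol and SAP*

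**What the plan says.** Section 12.2.1 defines one analysis population. For the injectable arm: "The Intent-to-treat (ITT) population will include all patients in the AL-LAI group who received at least one dose of AL-LAI". For the oral arm it takes patients "who filled at least one prescription of ARI-ORAL after random treatment assignment. This population will be used for efficacy and safety analyses". No time limit is set for the fill.

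No all-randomised set and no separate safety set appears in the Synopsis, Section 12.4 or Section 12.5. Section 12.2.2 adds adherence analyses, not another population. The primary objective (Section 5.1) compares patients according to the arm to which they were randomised.

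The abbreviation list treats AL-LAI and AL-NCD as separate products. On timing, Section 7.2.2 says: "The first AL-LAI injection may be administered on the same day as the one-day initiation regimen or up to ten days thereafter".

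On follow-up, Section 6.3 says that if the assigned drug is "discontinued and/or switched to a different antipsychotic medication, the patient may remain in the study until the 12-month assessment point". Nothing comparable is said about a patient who never starts it.

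**The concern.** Intent-to-treat means that everyone randomised is analysed in the assigned arm. Here, entry depends on something that happens after the patient and clinician know the assignment. The test also differs in kind: an injection given by staff in one arm, a pharmacy fill in the other. If patients who decline the injection, or never fill, differ in relapse risk from those who start, the two analysed groups are no longer the groups that randomisation made comparable.

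The tests also sort patients oddly. An oral patient who fills but takes nothing is included. One who uses tablets left over from Stabilization without a new fill is excluded. Leftovers are plausible, because everyone is on oral aripiprazole before randomisation (Section 7.2) and prescriptions usually cover 30 days (Section 9.2.2).

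Few events are planned. Section 6.4 allows over-enrolment "to ensure that there are at least 14 patients who had a relapse in the 12-month Treatment period", so one excluded relapse could matter if the result lies near the significance boundary.

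For safety, a patient who receives AL-NCD and stops before the first AL-LAI injection has been exposed to study drug but is outside the only safety set.

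**Working it through.** **Inputs from the plan.** 45 randomised and 36 completers per arm (Synopsis: "45 randomized patients (36 completers) in each group provides at least 80% power"); relapse 5% or 7.5% against 33%, with stated power 87% and 78% (Section 12.1.1); two-sided alpha 0.05 (Section 12.4); target of 14 relapses (Section 6.4). The number and risk of non-starters are not given, so every value of k and every non-starter risk below is an assumption.

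**1. The plan's own power.** Two proportions, pooled variance, n = 36 per arm:

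power = Φ[(|p1 − p2| − 1.96·s0)/s1], where s0 = √(2p̄(1−p̄)/n) and s1 = √([p1(1−p1) + p2(1−p2)]/n).

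- 5% vs 33%: (0.28 − 1.96 × 0.0925)/0.0864 gives 87.4%.
- 7.5% vs 33%: (0.255 − 1.96 × 0.0947)/0.0898 gives 78.0%.

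Both match the stated figures.

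**2. No true effect, exclusions from the injectable arm only.** Both arms have 33% risk, and k of 45 AL-LAI patients are never injected and are dropped. Risk left in the set = (45 × 0.33 − k × r)/(45 − k); HR = ln(1 − that risk)/ln(0.67).

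| k | r = 50% | r = 80% |
|---|---|---|
| 2 | 0.97 | 0.92 |
| 4 | 0.94 | 0.83 |
| 6 | 0.90 | 0.74 |

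**3. Planned effect, k exclusions in each arm.** Assume 5% among AL-LAI starters, 33% among AL-LAI non-starters, 33% over all oral patients, and that every oral non-filler relapses. All randomised: pL = [(45 − k) × 0.05 + k × 0.33]/45 against 0.33. Defined set: 0.05 against pO = (45 × 0.33 − k)/(45 − k). HR = ln(1 − pL)/ln(1 − pO).

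| k | All randomised: pL | HR | Defined set: pO | HR |
|---|---|---|---|---|
| 1 | 0.0562 | 0.144 | 0.3148 | 0.136 |
| 2 | 0.0624 | 0.161 | 0.2988 | 0.144 |
| 3 | 0.0687 | 0.178 | 0.2821 | 0.155 |

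The arms pull in opposite directions. With k = 3 in one arm only, moving from all randomised to the defined set changes the HR from 0.178 to 0.128 (AL-LAI exclusions) or from 0.128 to 0.155 (oral exclusions).

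**4. One relapse near the boundary.** Crude event split, z = (a − d/2)/√(d/4), with a oral relapses out of d in total:

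- 11 vs 4: p = 0.071; drop one AL-LAI relapse, 11 vs 3: p = 0.033.
- 11 vs 3: p = 0.033; drop one oral relapse, 10 vs 3: p = 0.052.

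Median Cox Wald p-values from 400 simulated trials (uniform event times, no attrition) are 0.061 to 0.036 for the first pair and 0.033 to 0.047 for the second. A log-rank test gives 0.049 to 0.023 for the first. Whether 0.05 is crossed therefore depends on the test.

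**5. Cost of including everyone.** Putting pL from step 3 into the step 1 formula, for k = 1, 2, 3:

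- 5% base: 85.3%, 83.0%, 80.6%.
- 7.5% base, with pL recalculated the same way (0.0807, 0.0863, 0.0920): 75.6%, 73.1%, 70.5%.

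**The case against.** The wording defect is hard to dispute; the case on the other side is about size.

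- **Exclusions may be very few.** Only patients who tolerated at least two weeks of oral aripiprazole are randomised, oral drug costs the patient nothing, late fills count, and AL-LAI can be given at the same visit as AL-NCD. Anyone who starts and later stops stays in the set. This stands, and it limits the likely bias. It also means that the correct definition would cost almost nothing.
- **The boundary splits are chosen to sit near 0.05.** The plan's rates on 36 per arm give 36 × 0.33 = 11.9 and 36 × 0.05 = 1.8 relapses. By the same crude formula, 12 vs 2 gives p = 0.008, and removing one relapse gives 0.002 (AL-LAI) or 0.013 (oral). This stands: if the assumed effect is real, one exclusion does not change the conclusion. For the second boundary pair, the simulated Cox medians also stay below 0.05.
- **The partial cancellation in step 3 rests on every oral non-filler relapsing.** At 50% risk, oral exclusions move the HR only from 0.128 to 0.130, 0.132 and 0.134 for k = 1, 2, 3. This stands, and it means cancellation cannot be relied on.
- **The power cost assumes that the prior 5% rate describes injected patients.** If it came from all randomised patients, non-starters are already counted and the loss does not arise. The documents do not settle this.
- **Safety events are not lost.** Section 7.4.12 says: "Continuous monitoring of AEs will take place from the time a patient signs the informed consent document". Section 7.4.9.1 adds: "Semi-annual review of all safety assessment responses will be conducted by a Data and Safety Monitoring Committee at UCLA". This stands; the gap is in the set used for tabulation and comparison, not in collection or oversight.

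**Conclusion.** The concern holds. The population in Section 12.2.1 is a modified intent-to-treat set under the wrong name. It does not match the objective in Section 5.1, and it is the sole basis for both efficacy and safety analysis. That conclusion rests on the text and needs no assumption.

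The effect on the result is unknown in size and direction. It is zero if every patient starts, probably small if few do not, and could matter if non-starters are several, unequal between arms or at unusual risk. The figures in the working are illustrations under assumed counts and risks, not estimates for this trial. The point should be fixed, ideally before outcome data are examined, but nothing here shows that the planned comparison would be overturned.

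**What to change.** In Section 12.2.1:

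1. Define the intent-to-treat set as all randomised patients, analysed by assigned arm, and use it for the primary Cox model and the mixed models for MCCB and GFS: Role.
2. Keep the present definition as a sensitivity analysis, labelled modified intent-to-treat.
3. Define a safety set of all patients who received any study drug after randomisation (AL-NCD, AL-LAI or oral aripiprazole). State whether patients are grouped as assigned or as treated, and how exposure during Stabilization is reported.
4. Add one sentence, for example in Section 6.3, that randomised patients who never start the assigned drug stay in the scheduled assessments. The present text covers only discontinuation and switching.

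The cost is wording plus follow-up of any never-starters, for whom two-weekly BPRS visits are already scheduled. The planned number randomised does not change. The statistical price is dilution: about 2 to 7 percentage points of power for 1 to 3 AL-LAI non-starters at 33% risk (87.4% to 80.6%, or 78.0% to 70.5% in the conservative case), and none if everyone starts.
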